7 STUDY PROCEDURES

7.1 Recruitment

Potential participants for all sections of the study (Feasibility study included) will be identified via outpatient clinics in the Rheumatology and Pain Relief Unit within the Oxford University NHS Trust, or Connect Health (clinical stakeholder organisations with a responsibility to assess and manage patients within the NHS). Where possible, a member of the clinical care team will pre-screen clinic lists to highlight potentially suitable participants in advance of a clinic appointment. Potential participants will be initially approached by their clinical care team and provided with a participant information leaflet. If the potential participant agrees, the clinician will also pass on the preferred patient contact details to the research team. Posters, with contact details for the research team, will be put up in relevant waiting

areas so that potential participants can ask their clinician about the study and/or contact the research team directly.

The research team will arrange to contact all potential participants, either in person, by email or by telephone, to give them the opportunity to ask any further questions regarding the study. If the participant would like to enrol in the study, the researcher will organise a suitable time for the participant to confirm eligibility for the study, and if suitable take informed consent from the participant.

7.2 Screening and Eligibility Assessment

Screening for all sections of the study (feasibility study included) will involve confirming the participants age, assessment of vulnerability, understanding of English, clinical musculoskeletal diagnosis, and review of the general medical history. Additional MRI safety screening will be conducted in participants willing to undertake the MRI component of the study. This will include questions regarding their suitability to enter an MRI scanner. For the feasibility study additional sleep related screening will be conducted. Screening may be done in person if a participant is attending the hospital for a routine appointment, or by telephone, email or using Microsoft Forms. The participant will be allowed up to one week to consider the information, and the opportunity to question the Investigator, their GP or other independent parties to decide whether they will participate in the study. The restriction of one week is due to the fact that if the patient is due to start on a new treatment, time will be needed to arrange the baseline assessment prior to them starting their new medication. In the case of participants with fibromyalgia who are being referred for pain rehabilitation treatment, there will be more time available, as the waiting time for this is much longer (often up to 6 months). If confirmation of eligibility to participate in the main study and feasibility study is in person, a paper copy of the Participant Information Sheet will be given. If confirmation of eligibility to participate is by phone, a paper copy of the Participant Information Sheet can be posted or emailed. MRI safety screening will be repeated on the day of participation prior to entering the scanner.

7.3 Informed Consent

Written and verbal versions of the Participant Information and Informed Consent will be presented to the participants detailing no less than: the exact nature of the study; what it will involve for the participant; the implications and constraints of the protocol; the known side effects and any risks involved in taking part. It will be clearly stated that the participant is free to withdraw from the study at any time for any reason without prejudice to future care, without affecting their legal rights, and with no obligation to give the reason for withdrawal.

The participant will be allowed up to one week to consider the information, and have the opportunity to question the Investigator, their GP or other independent parties to decide whether they will participate in the study. The restriction is due to the fact that if the patient is due to start on a new treatment, time will be needed to arrange the baseline assessment prior to them starting their new medication. In the case of participants with fibromyalgia who are being referred for pain rehabilitation treatment, there will be more time available for the participants to decide, as the waiting time for this is much longer (often up to 6 months). They can choose which of the further assessments they would like to participate in, if at all, whilst they are waiting for their pain management treatment.

Once eligibility and intent to take part in the study have been confirmed by the Chief Investigator or delegated study personnel and the potential participant can personally sign and date the latest approved version of the Informed Consent form before any study specific procedures are performed, or remote consent can be taken over the telephone by the researcher. The paper consent form or remote consent form will be photocopied and a copy given, emailed or posted to the participant for their own records. The original will be filed in the study site file and another copy scanned into the participant's medical records.

At the point of consent, participants with fibromyalgia can choose to additionally participate in the feasibility study (see section 7.5).

7.4 Baseline Assessments

At the baseline assessment visit, participants will be asked to complete the clinical assessment and validated questionnaires described below. This will be done using REDCap, a secure web application online portal (redcap) where possible, either with the researcher present or independently according the participants preference. If required, a paper format will be used:

Assessment	Purpose
Clinical history	This will include disease duration, current and previous treatments including those for pain management specifically, and other past medical history
Disease activity score measure	Used in routine clinical practice to capture disease activity specific to a condition. For example: disease activity score-28 in rheumatoid arthritis, psoriatic response criteria in psoriatic arthritis, Bath ankylosing spondyloarthritis disease activity index in ankylosing spondyloarthritis, fibromyalgia impact questionnaire in fibromyalgia)
MRI safety questionnaire	Assess whether participant is safe to undergo MRI scanning
Euroqol-5D (EQ5D)/HAQ	Standardised measure of health-related quality of life
Musculoskeletal Health Questionnaire (MSK-HQ)	Supplementary measure of health status designed to be used across a range of musculoskeletal conditions in order to monitor progress over time and response to treatment
Beck depression and anxiety inventories	To assess and describe psychological comorbidity and its impact on symptoms and treatment response
PainDETECT questionnaire	To assess for features of neuropathic pain
Central sensitivity inventory	To indirectly assess centralised sensitisation
Insomnia severity index	To assess sleep disturbance, an important factor in pain experience

Fibromyalgia survey criteria	To assess for concurrent fibromyalgia in those with inflammatory arthritis, which may impact treatment outcome
Fibromyalgia Impact Questionnaire Revised*	To assess the overall impact of symptoms and
	quality of life in those with FM in Sleep sub-study
Chalder Fatigue Scale*	To assess self-reported fatigue in Sleep sub-study
Behavioural inhibition system/Behavioural	To assess reward responsiveness which may be
activation system (BIS/BAS) scale	impaired in chronic pain and impact on treatment responsiveness
The Multidimensional Assessment of	To assess interoception which may be impaired in
Interoceptive Awareness (MAIA)	patients with chronic pain
Locus of control	To quantify the degree to which participant feels
	they have control over outcome of life events
	which is likely to be particularly relevant to
	response to rehabilitation
Credibility Expectancy Questionnaire	To assess expectations of treatment so can adjust for this effect
Tampa scale for kinesophobia	To assess fear of movement which may impact
	response to treatment
British Columbia Cognitive Complaints Inventory	To assess self-reported cognition in Sleep sub-
(BC-CCI)*	study
Multiple Ability Self-Report Questionnaire	This is a measure of self-perceived cognitive
(MASQ) *	difficulties that is more widely used in the
	fibromyalgia literature to explore subjective
	cognitive difficulties (i.e. Fibro-fog). The BC-CCI
	(outlined above) is used in the sleep literature to
	explore subjective cognitive difficulties. Using
	both will allow us to compare our results to
	previous work in both the fibromyalgia and sleep fields
Pittsburgh Sleep Quality Index (PSQI)*	Provides quantitative sleep parameters, such as
	total sleep time, wake-after-sleep onset
Epworth Sleepiness Scale (ESS)*	A measure of subjective sleepiness
Sleep Disorders Questionnaire*	To screen for sleep disorders which may be an
	exclusion for participation, such as obstructive
	sleep apnoea, restless leg syndrome etc (these
	are already outlined in the exclusion criteria
	(section 6.3))

^{*} Additional questionnaires if participant consent to the feasibility study

Tasks

Participants will undergo quantitative sensory testing outside the scanner in accordance with the established protocol developed by Rolke and the German Research Group on Neuropathic pain. Quantitative sensory testing is a standard technique used to determine skin sensitivity to thermal, touch, and vibration stimuli. Testing will be conducted over an area which is primarily affected by the musculoskeletal condition of interest (e.g. metacarpophalangeal joints in rheumatoid arthritis), as well as control areas that are not directly involved (e.g. sternum). The exact protocol and test sites will be refined following pilot work in up to 5 participants, in order to ascertain which modalities and test sites

The Chief Investigator, or any other trained investigator, will draw max 30mls blood via venepuncture as per the World Health Organisation (WHO) guidelines on drawing blood. The appropriate equipment, including tourniquet, latex/nitrilegloves, vacutainers, sterile needles, cotton wool, alcohol wipes, plasters, clean equipment trays and medical tape will be available in the clinical testing room within the MRI scanning research facility. The room has a comfortable chair for participants with a cushion/pillow/arm rest to support participants' arms while blood is being drawn, and a clinical examination bed where the participant can lie down (with their legs raised if necessary) should they feel faint. Lastly, basic facilities for dealing with participants who faint (or feel faint) during phlebotomy will be provided—somewhere they can lie down and equipment for monitoring blood pressure. There will always be another member of staff in the building whilst this procedure is being performed. There is an appropriate sharps disposal bin in the room. The facility has a needle stick policy in place. The sample will be taken labelled with the participants' ID number. After the participant's appointment, the sample will be taken to the laboratory and will be either processed immediately and/or stored at in a locked freezer at -80 or -20 degrees, in compliance with The Human Tissues Act. Although taking blood is a very standard procedure, common risks are pain during the procedure and bruising (with associated pain afterwards), these will usually disappear within a few days. In the event that a participant reports symptoms of an infection (local redness, swelling, pain or discharge of pus) or other complications, they should be referred to their GP or to A&E urgently. The time required for taking the blood sample is 3 minutes.

Overall, the Baseline Assessment visit will take around 2 hours. Participants will be able to stop at any point and continue after they have had a rest.

Feasibility Study

Recruitment into the feasibility sub-study will be as the procedure described in section 7.1. At the point of consent, participants with fibromyalgia who have chosen to additionally take part in the feasibility study, will be randomised 1:1 to Sleepio or Standard Care, using the Sealed Envelope randomisation software (www.sealedenvelope.com).

The baseline assessment will be the same as for the main study, with a very short QST protocol lasting up to 5 minutes only. In addition, participants will be asked to complete a vigilance task using the study device and the research team will help the participant to capture video data for motor evaluation.

Motor evaluation

Video data of participants doing simple physio exercises, to quantify how they move doing standardised movements. This is done using a smart-phone / tablet camera, which people can set up in their home or attend for a separate study visit. The participant (face included) is recorded doing a list of exercises - marching on the spot holding onto a chair for support, hip and knee extension, squats and heel lifts with chair for support. These typically involve 3 to 4 repetitions and takes a few minutes, after which the video will be uploaded to a secure cloud-server. Motion capture analysis will use inhouse software, owned by the University of Oxford but based on Detectron2

(https://github.com/facebookresearch/detectron2), that allows quantification of movement angles and speeds at different joints, as a metric of physical ability, which can be used to quantify pain related changes in movement; these will be visually inspected for validation. The videos themselves will not be stored but the computer generated skeletal poses will be stored as 2D/3D coordinate time series in pkl or h5 files (see Reconstruction, Figure 1).

Participants will be given information on how to access the maladaptive learning games and cognitive tests, which they can complete at home at their convenience.

Patients will be given an activity watch to wear, and a sleep diary to complete, for 7 days before and after undergoing the Sleepio programme or standard care.

After the visit, participants will then be randomised to standard care or given access to the online CBT-I programme, Sleepio. Participants will be given a web link and activation code to Sleepio. They will be required to complete a daily sleep diary for the duration of the programme. The programme involves six personalised 20-minute video sessions over 10 weeks. It uses evidence-based cognitive and behavioural interventions, sleep hygiene education, and relaxation exercises to target unhelpful behaviours and thoughts in order to reduce symptoms of poor sleep. Participants may use Sleepio in their own time at home via a web browser or smartphone app. Standard care involves provision of written materials produced by the charity Versus Arthritis, with evidence-based advice on sleep hygiene.

Maladaptive Learning

Patients with fibromyalgia can choose to participate in a battery of online learning games that can be played on tablet or smart phone on a separate day. These are validated experimental tasks that probe how people learn and make decisions for rewards (e.g. winning points in a game) and punishments (e.g. losing points in a game). The different games probe different aspects of learning, and each takes around 20 minutes; the score is revealed at the end. The games are as follows:

- 1i) Balloon popping game (Instrumental learning task). Coloured balloons rise up on the screen, and on each go, participants choose one which balloon they want to pop by touching it on the screen. When a balloon pops it will either give them points, or take away points, or do nothing. Participants can learn which coloured balloons are good and which are bad, but the tricky thing is that this changes continually through the game, so they need to constantly keep track and relearn which ones are good. We analyse in detailed the learning process by looking at people's choices and response times.
- ii) 'Road sign check' game (Generalization task). People imagine they are driving through a dangerous mountain road and pass road signs which are symbols on a sign background the signs mean that it is either safe, or that there is a danger they need to avoid by pressing a button. The problem is that the signs are very similar and can be hard to tell which ones are safety and which are danger signs. Furthermore, you lose points for pressing the 'avoid' button. Therefore you need to look very carefully and only press 'avoid' when you think the sign is a danger sign. The task itself involves a blending of visual features of two exemplar signs, and allows us to assess how people generalise across perceptual space.
- iii) Screen touching game (Motor decision-making). Two 'target zones' appear on a screen a green target, and a red target. If you touch inside the green target you win points, if you touch inside the red, you lose points. The participant needs to touch as quickly as possible, as the targets only appear for a very short time. The problem is that the two targets often overlap, and are often very small, meaning that you need to be both very quick and very accurate typically trying to touch within the green target that does not overlap with the red, which might only be a slither of the target. We analyse how people's movement actions are affected by the proximity of the red target, given their overall level of accuracy.
- iv) Ball balancing game (Motor adaptation). In this game, participants need to hold their phone/tablet horizontally to balance a virtual ball on the screen and stop it rolling off. To make things difficult, there is a constant moving tilt to the screen which they can't see, so they need to concentrate and constantly adjust the way they hold the phone/tablet to stop it rolling off. We analyse how they adjust their movements to different tilts.
- v) Prediction games. There are two version of the games: a pain prediction game and a control task, a stockmarket prediction game. In the pain prediction game, participants are required to continuously rate their spontaneous level of pain on a visual analogue scale. Intermittently they will be asked to predict how much pain they expect to feel in the near future, again using another visual analogue scale. Participants are asked to rate the confidence in their estimates. In the control stockmarket task, participants are asked to predict the value of shares changing over time, as in the real-life stockmarket. Again, we will collect confidence ratings for the prediction estimates. The first task evaluates how pain evolves over time, in each subject, and the ability of participants to consciously anticipate pain flare-ups. The control task is used to assess whether there are specific difficulties in anticipating uncertain events involving rewards and losses.

7.5 **Subsequent Visits** – main study

Participants will be followed up at up to four timepoints, as shown in the flowchart in section 5. The questionnaire component can be completed using REDCap, a secure web application, or paper format as preferred by the patient. If the participant is unable to attend for an in-person visit, the questionnaire component of the assessment will be completed either by telephone, using REDCap, or the questionnaires may also be posted to the participant for completion, if this is preferred by the participant. Follow up visits at T2 (10-14 weeks after commencing therapy) and T3 (22-26 weeks after commencing therapy) will be identical, as detailed below:

Follow-up T2 and T3*

The following assessments will be conducted**:

- Repeat eligibility check
- Assessment of disease activity measures and other validated questionnaires listed in baseline assessment
- Update of medical history, medications, and any other therapeutic strategies being used
- QST/brain imaging if conducted at baseline

A further follow-up visit T4 will be conducted at 50-54 weeks after commencing treatment this will include. The following assessments will be conducted**:

- Repeat eligibility check
- Assessment of disease activity measures and other validated questionnaires listed in baseline assessment
- Update of medical history, medications, and any other therapeutic strategies being used

*In patients with inflammatory arthritis, commencing a biologic therapy, an additional follow up assessment will be conducted at 1 month. This will be identical to the one conducted at follow-up T2 and T3.

**If the participant is unable to attend for an in-person visit, a telephone appointment will be offered in order to complete the questionnaires. The questionnaires may also be posted to the participant for completion, if this is preferred by the participant.

Subsequent Visits – Feasibility study

The follow up at T3 can be conducted remotely. Questionnaires, cognitive testing and maladaptive learning assessments will be completed online and the activity watches will be administered and returned by recorded delivery post. Participants will also be invited by telephone or email to attend a follow up research visit in person, which will be the same as the baseline assessment.

Focus groups

Three groups of 6 participants (18 in total) will be invited to participate in a focus group at T3 (24 weeks). This will be a part of the consent process for this feasibility-study, and participants may opt not to take part. The focus groups will be approximately 3 hours in length, and participants will be reimbursed for their time in accordance with INVOLVE guidelines. These focus groups will be carried out online, using Microsoft Teams, and the recording will be transcribed using MS Teams inbuilt transcription software. Participants in these focus groups will be asked about their views of the study process, with the aim to identify barriers and facilitators to a future definitive trial of the intervention.

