4. OBJECTIVES AND OUTCOME MEASURES

Objectives	Outcome Measures	Timepoint(s) of evaluation of this outcome measure (if applicable)
Primary Objective To investigate whether patients with inflammatory arthritis and features of centrally driven pain have reduced chance of responding to treatment.	Percentage achieving Disease Activity Score <2.6. Other measures include Disease Activity Score reduction of >1.2; simple disease activity score <3.3; Clinical Disease Activity Index ≤2.8; American College of Rheumatology (ACR)/European League Against Rheumatism (EULAR) Boolean (28 tender joint count,28 swollen joint count, patient's global assessment (0−10 scale),CRP (mg/dL), all ≤1), modified DAPSA<4.	Baseline and at 3, 6 and 12 months after commencing therapy.
Secondary Objectives To investigate the features of centrally driven pain, detected through multi-modal assessment, in patients with a range of musculoskeletal conditions.	Scoring according to: Central Sensitivity Inventory, Fibromyalgia survey criteria, PainDETECT questionnaire alongside neuroimaging findings.	Prior to commencing therapy
To investigate whether patients with features of centrally driven pain have differences in NfL, inflammatory markers and genes which can prospectively identify prognostic factors for developing neuropathic pain, its persistence and/or its severity	Blood test	Baseline
To investigate whether digital CBT-I can improve quality of life and centrally driven symptoms in people with FM	SIQR, sleep actigraphy, sleep diary, online cognitive assessment, self-reported cognitive function (British Columbia Cognitive Complaints Inventory, BC-CCI) Neuroimaging (brain MRI)	Baseline, 12 weeks and 24 weeks Baseline and 12 weeks

To investigate the cost effectiveness of digital CBT-I	EQ-5D-5L Healthcare usage dairy	Baseline, 12 and 24 weeks
To determine barriers and facilitators to a definitive trial of CBT-I to alleviate symptoms in people with FM	Focus groups of participants	24 weeks
To investigate whether maladaptive learning in the brain plays a role in chronic musculoskeletal pain, and from this to predict treatment response in fibromyalgia patients		Baseline, 12 weeks
	Online games to include learning and decision-making, generalisation/ avoidance, motor decision-making, and prediction/metacognition tasks, and motor (movement) evaluation - videobased assessment measuring movement	
	during standardised physio-type exercises	

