3.2 Randomisation and Blinding

Patients will be randomised after consent and collection of baseline data. Participants will be randomised on a 1:1 basis using *Sealed Envelope*, a secure electronic randomisation platform. To ensure balanced group allocation, randomisation will be stratified by sex and completion of a brain MRI in the neuroimaging sub study, with participants assigned in blocks of 10. Outcome assessors will be blinded to treatment allocation for all study visits and communications with participants, and investigators carrying out analysis will also be blinded. Due to the nature of the intervention, participants were unable to be blinded.

To maintain allocation concealment, all study investigators will not have access to future group allocations and are unable to influence randomisation. The treatment allocation will be communicated to participants by an independent research nurse who is not involved in study visits or outcome assessments via email. This email will consist of scripted phrases and contained instructions for *Sleepio* access. In addition, the research nurse will act as an intermediary for any queries regarding the treatment or group allocation, and will relay questions regarding the intervention to the investigators anonymously to preserve blinding.

Due to the nature of the intervention, blinding participants was not possible. However, the outcome assessors will remain blinded to treatment allocation throughout the trial. Participants were instructed not to disclose their group assignment to study investigators during follow-up visits to maintain blinding. Participants cannot be blinded to their treatment. The outcome data will be collected directly from the participant. Outcome assessors will be blinded to the participant's treatment allocation.

Full details of the randomisation are available in se_list_242996464514928final, stored in the confidential statistical section of the TMF. No emergency randomisation plan was developed for this study.

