Cognitive testing: Cognitive testing will be performed at the baseline (pre-randomisation) and posttreatment (3-month) study visits. As one of the principal symptoms of 'fibrofog' is concentration difficulties, a test of sustained visual attention was carried out during the visit(Zhao et al. 2022). This test was selected as previous studies have found deficits in sustained attention in patients with brain-fog symptoms post-COVID, which phenotypically may resemble the cognitive symptoms seen in fibromyalgia(Zhao et al. 2022). This was performed during the visit on an Apple iPad with attached keyboard on a Google Chrome browser. The task involved pressing the spacebar when '0' appeared amidst other digits (1-9), masked by a semitransparent grey checkerboard. Each block lasted 60 seconds, and after a practice block, 9 blocks were performed in total. The hit rate was calculated from correct hits, while false positive rate was calculated from incorrect hits. A composite measure of task accuracy, D', is derived. Reaction time (RT) for correct hits is measured as the time between the digit appearing on the screen and the spacebar being pressed. RT variability is also assessed.

Health-related quality of life: Quality of life will be measured pre-randomisation (baseline), and at 3-, and 6months via the REDCap electronic survey tool. For the planned economic evaluation, the EuroQol-5D-5L (EQ-5D-5L) will be used to estimate quality adjusted life years (QALYs), which are measures on a scale of -0.59 to 1.0, where 1.0 is a full year of perfect health. The adult value set for the UK will be used to estimate QALYs.

Healthcare resource utilisation: healthcare utilisation will be measured pre-randomisation (baseline), and at 3-, and 6-months via the REDCap electronic survey tool. For the planned economic evaluation, participants will report their healthcare service use over the previous 3 months, including hospital visits, medical imaging, and consultations with healthcare professionals (e.g., GPs, nurses, physiotherapists). Information was also collected on medications, unpaid caregiving, social services, and the financial impact of the condition on relatives and friends, including out-of-pocket expenses for care, transportation, and medical treatments.

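### Home cognitive tests and learning games have no completion deadline, so their baseline can be recorded after open allocation and possibly after Sleepio has begun

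*Protocol*

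**What the plan says.** **Outcomes.** For the dCBT-I objective, Protocol Section 4 lists "SIQR, sleep actigraphy, sleep diary, online cognitive assessment, self-reported cognitive function" with a baseline value and repeats at 12 and 24 weeks. The learning games are listed there at baseline and 12 weeks.

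**Home testing.** Protocol 7.4 (Feasibility Study) says that participants receive access information for "the maladaptive learning games and cognitive tests, which they can complete at home at their convenience". Under Maladaptive Learning, the same section describes "a battery of online learning games that can be played on tablet or smart phone on a separate day". One cognitive measure is done at the visit itself: "participants will be asked to complete a vigilance task using the study device".

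**Randomisation.** The documents give three timings.
- Protocol 7.4, Feasibility Study, opening paragraph: "At the point of consent, participants with fibromyalgia who have chosen to additionally take part in the feasibility study, will be randomised 1:1".
- Protocol 7.4, after the visit procedures: "After the visit, participants will then be randomised to standard care or given access to the online CBT-I programme, Sleepio".
- SAP 3.2: "Patients will be randomised after consent and collection of baseline data".

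**SAP cognitive outcome.** SAP 6.1 states: "Cognitive testing will be performed at the baseline (pre-randomisation) and posttreatment (3-month) study visits". The measure it describes is the sustained-attention (vigilance) task done during the visit.

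**The concern.** A baseline is useful for adjustment because it precedes allocation. Participants in this trial are unblinded. If one of them does the home tests after learning the arm, effort can depend on the arm. If Sleepio has also begun, the value may already contain part of the treatment effect. Adjusting for that value, or subtracting it, then removes part of what the comparison is meant to estimate.

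Delay is plausible. Protocol 7.4 describes five types of game at about 20 minutes each, on top of a visit of about 2 hours. The feasibility study selects people with disturbed sleep and difficulties with concentration or memory (Protocol 6.2).

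What is at stake is the arm comparison on the online cognitive assessment and the learning games. Cognition is a stated aim of the feasibility study (end of Protocol Section 3).

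**Working it through.** **1. Order of events under each statement**

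| Source | Randomisation | Can a home baseline follow allocation? |
|---|---|---|
| Protocol 7.4, opening paragraph | At consent | Yes: every baseline measure would follow it |
| Protocol 7.4, later paragraph | After the visit, with Sleepio access | Yes: home tests also follow the visit and have no deadline |
| SAP 3.2 | After baseline data | Only if the home tests are not counted as baseline data |

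**2. Does SAP 3.2 cover the home tests?** SAP 3.1 describes the baseline data as an online survey (demographics and questionnaires) plus site-visit measures, including cognitive performance. Home games and home cognitive tests are not named there, nor among the outcomes in SAP 6.1 and 6.2. The SAP therefore does not clearly close the gap.

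**3. What is not affected.** FIQR and the vigilance task are both labelled pre-randomisation in SAP 6.1, and both documents place a vigilance task at the visit. The primary sample size does not depend on this point and reproduces:
- difference 0.14 × 57.694 = 8.077; d = 8.077 / 18.688 = 0.432; 85 per arm;
- 85 × (1 − 0.75²) = 37.19; 37.19 / (1 − 0.033) = 38.5, rounded up to 39 per arm, 78 in total.

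**4. Illustration of the mechanism.** Let d be the true standardised effect, r the baseline–outcome correlation, p the share of the Sleepio arm testing late, and f the share of the eventual effect already present at that test. The baseline means then differ by p × f × d. With equal SDs the regression slope is about r, so:

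- baseline-adjusted estimate ≈ d − r × (p × f × d) = d(1 − r p f);
- change-from-baseline estimate = d(1 − p f).

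Inputs: d = 0.3 is the threshold in Protocol 9.2. r = 0.75 is the FIQR correlation from SAP 3.3, borrowed here because none is given for the home tests. p and f are pure assumptions.

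| p | f | Adjusted, 0.3(1 − 0.75 p f) | Loss | Change score, 0.3(1 − p f) | Loss |
|---|---|---|---|---|---|
| 0.25 | 0.25 | 0.286 | 5% | 0.281 | 6% |
| 0.5 | 0.5 | 0.244 | 19% | 0.225 | 25% |
| 1 | 0.5 | 0.188 | 38% | 0.150 | 50% |

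A simulation of ANCOVA (40 per arm, 15,000 runs per case) gave 0.288, 0.247 and 0.189 for the adjusted estimate, in line with the formula. Over r from 0.5 to 0.75, p from 0.25 to 1 and f from 0.1 to 0.5, the adjusted loss runs from about 1% (0.5 × 0.25 × 0.1 = 0.0125) to 37.5% (0.75 × 1 × 0.5). The width of that range shows that the size cannot be stated from the documents.

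**The case against.** **No planned model uses these baselines.** The constrained longitudinal model in SAP 6.2 applies to FIQR and a named list of secondary outcomes, whose only objective cognitive measure is the in-visit vigilance task. Protocol 9.1 gives descriptive summaries for the feasibility outcomes and parameter fitting for the games. This stands. A reader might infer that the trial's main result, or the SAP's cognitive result, is biased; the documents do not support that. The risk is to any between-arm analysis of the home measures using their baseline, which Section 4 invites by listing baseline and follow-up values under the objective of improving symptoms.

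**The listed online assessment may be the vigilance task.** Section 4 does not name the task, and SAP 6.1 runs the vigilance task in a browser. This is possible for the cognitive assessment. It does not help the games, and Protocol 7.4 speaks separately of cognitive tests done at home.

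**There may be time before Sleepio starts.** Protocol 7.4 asks for 7 days of watch and diary before the programme or standard care, which leaves about a week if it falls after the visit. That weakens the claim that Sleepio has begun, but it does not require the home tests to be done in that week. SAP 6.1 instead times the actigraphy before the baseline visit.

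**Large early effects are unlikely.** The programme runs over 10 weeks (Protocol 7.4), and SAP 5.5 places its core component in session 3. Half the effect being present at a late baseline, in every Sleepio participant, is an extreme case. This stands.

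**Predicting response.** A reader might infer that early response to Sleepio would act as its own predictor in the learning objective. The documents do not show this. That objective concerns fibromyalgia patients generally, the games are optional, standard treatment is pain rehabilitation after about a 6-month wait (Protocol Section 5), and nothing says that the predicted response is to Sleepio.

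**Conclusion.** The point holds for the protocol's home cognitive tests and learning games. A site following Protocol 7.4 as written can record their baseline after open allocation and possibly after Sleepio has begun. SAP 3.2 would prevent this only if its baseline data include the home tests, which it does not say. The three statements on randomisation timing are also unreconciled.

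The bias would affect any baseline-adjusted or change-from-baseline comparison on these measures. Its size is unknown. The 5% to 38% in the illustration should not be read as an estimate of the loss in this trial, because p and f are assumed and r comes from a different measure. Actual contamination may be small. FIQR and the in-visit vigilance outcome fall outside the point. The correction is still worth making because it is specific and cheap, and it concerns protocol-listed outcomes.

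**What to change.** 1. Reconcile the two statements in Protocol 7.4 with SAP 3.2, so that randomisation follows baseline collection throughout.
2. State in Protocol 7.4 that the home baseline tests and games must be completed before the allocation is released, or within a short fixed period (for example 14 days) after which allocation proceeds and the baseline is recorded as missing. State in SAP 3.2 that baseline data include these tests.
3. In the analysis, compare each test's time stamp with the randomisation date, report the number of late tests by arm, and do not use post-randomisation tests as baseline.

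The planned study period ends on 30 April 2025 (Protocol synopsis) and SAP V1.1 is dated 29 April 2025 (SAP 1.2). Recruitment status is not stated. If recruitment has closed, step 2 comes too late to change data collection, but step 3 still applies.

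The cost is a few sentences, a check before randomising, a short delay for some participants and a few missing baselines.
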